7.1.3 STANDARD OF CARE STUDY PROCEDURES

Current guidelines recommend annual imaging to detect asymptomatic stone activity (formation or growth) for individuals with urinary stone disease. Study participants may undergo low dose CT scan (renal ultrasound for study participants age < 18 years at enrollment) at 12 months as part of standard

of care monitoring for their urinary stone disease, or as a part of a surgical procedure to remove a stone. Results of these studies may be available through the treating physician. Data from other stone-directed imaging studies performed at the direction of the participant's treating physician at 12 (+/- 1) months and throughout the study follow-up period may also be collected.

7.1.4 BIOREPOSITORY SPECIMEN COLLECTION

In addition to study-specific laboratory tests, blood, urine and stone samples as well as stool samples will be obtained for use in future studies. These samples along with the study data (including digital imaging data) will be stored in the NIDDK Repositories, supported by the National Institutes of Health. These data and stored samples will be available to use in research for the study of USD after PUSH is complete.

Biospecimens collected as part of the study will include:

- Whole blood (DNA)
- Serum
- Plasma
- Urine
- Stool
- Kidney stone sample (if available)

7.1.5 DATA COLLECTION PROCESS

Study data from these sources will be integrated at the SDRC.

Clinical Centers/Sites: Clinical Center/site personnel will complete eCRFs (in the EDC database managed by the SDRC) during the study period covering participant eligibility and baseline information, outcome events, study procedures (other than 24 hour urine collection), and safety monitoring (see Section 8).

Way to Health: The study will leverage the NIH-funded Way to Health web-based platform at the University of Pennsylvania (UPENN) (RC2-AG036592-01). This platform for clinical trials implementation provides a secure, efficient, user-friendly approach to monitoring participation, delivering feedback/communications (e.g., through emails, texts or phone messages using Automated Interactive Voice Response) and incentives in an automated fashion. All USDRN CCs will leverage the existing Way to Health infrastructure through administration of financial incentives and collection of fluid consumption data in real-time. These data will be securely transmitted to SDRC periodically as specified in the PUSH Manual of Procedures and the SDRC/WTH Data Transfer Agreement.

Hidrate Spark: Data regarding participants' daily fluid intake will be securely transmitted to Way to Health on a daily basis. All participants in the intervention arm will have their data transferred. Only participants in the control arm who choose to set-up their smart water bottle will have data transmitted.

Core Lab: 24-hour urine collections will be processed at a core lab facility for the USDRN, located at University of Texas Southwestern. Results will be securely transmitted to SDRC periodically as specified in the PUSH Manual of Procedures and the SDRC/UTSW Data Transfer Agreement.

All data and records generated during this study will be kept confidential in accordance with Institutional policies and Health Insurance Portability and Accountability Act (HIPAA) on study participant privacy. Investigators and other site personnel will not use such data and records for any purpose other than conducting authorized research. IRB approvals will be obtained prior to initiating study activities.

7.2 LABORATORY PROCEDURES/EVALUATIONS

7.2.1 CLINICAL LABORATORY EVALUATIONS

Study participants will complete periodic clinical laboratory evaluations, as outlined in the Schedule of Events Table (7.3).

These will include 24-hour urine volume, 24-hour urine analysis (calcium, creatinine, citrate, phosphorous, pH, sodium, urea nitrogen, oxalate, chloride, ammonium, magnesium, potassium, uric acid, sulfate, qualitative cystine[baseline]) and 24-hour urine osmolality. Supersaturations of calcium oxalate, calcium phosphate and uric acid will also be included. Urine Hcg will be performed on adult females of childbearing potential in association with CT scans, only; when a waiver of imaging is granted, this testing is also waived. Serum chemistry and osmolality will be obtained on participants without recent test results.

7.2.2 OTHER ASSAYS OR PROCEDURES

Study participants will undergo baseline and end-of-study imaging (low dose CT for participants aged \geq 18 years, renal ultrasound for those aged < 18 years at enrollment; imaging procedure details in Manual of Procedures) during the study, as outlined in the Schedule of Events Table (7.3). Historical records will be accepted in place of the baseline CT scan, as explained in Section 7.1.1. Waivers of imaging will be allowed, as explained in Section 7.1.1.

7.2.3 SPECIMEN PREPARATION, HANDLING, AND STORAGE

Specimen preparation, handling and storage will be in accordance with the PUSH Manual of Procedures and the clinical centers' institutional procedures.

7.2.4 SPECIMEN SHIPMENT

Specimen shipment for study specimens and specimens collected for the NIDDK Repository shall be shipped according to the procedures outlined in the PUSH Manual of Procedures.

7.3 SCHEDULE OF EVENTS TABLE

Procedure	Screen	Baseline	2 weeks ± 7 days	3 mos ± 30 days	6 mos ± 30 days	9 mos ± 30 days	12 mos ± 30 days	15 mos ± 30 days	18 mos ± 30 days	21 mos ± 30 days	24 mos ± 60 days
Informed Consent	X										
Email/Telephone Follow Up				X	X	X	X	X	X	X	X
Serum chemistry/eGFR	X										
Serum osmolality	X										
Hcg (urine dip)α		X									X
Randomization		X									
Provide smart water bottle*		X									
24-hour urine panel [†]	X [†]	X [†]									X
24-hour urine TV	X‡		X		X°		X°	X°			X°°
24-hour urine Cr	X‡		X		X°		X°	X°			X°°
24-hour urine osm	X‡		X		X°		X°	X°			X°°
Imagingα		X					X§				X~
Medical History	X										X
Weight and Height		X		X	X	X	X	X	X	X	X
LUTS assessment		X			X		X		X		X

* All participants are provided with a smart water bottle, but only participants randomized to the intervention arm are required to set-up the bottle and use it during the study.

†24-hour urine panel includes: calcium, creatinine, citrate, phosphorous, pH, sodium, urea nitrogen, oxalate, chloride, ammonium, magnesium, potassium, uric acid, sulfate, qualitative cystine. Qualitative cystine will only be performed for Week 2 collection. A Screening/Baseline 24 hour urine panel will only be done if the participant does not have the historical panel results needed for determining eligibility (see Section 7.1.1).

‡A single 24-hour urine sample will be collected at screening for participants without any 24-hour urine tests in the 12 months prior to the Screening visit and the central lab will run urine volume, creatinine and osmolality only on this sample. For participant with prior 24-hour urine tests but without the results listed in Section 7.1.1, a new sample will be collected at screening and the full panel will be run on this sample.

° For Months 6, 12, 18, a clinical 24 hr urine can be used in place of a new collection provided it is within the ±30 day window of that visit and it includes volume and creatinine.

°° For Month 24, a clinical 24 hr urine can be used in place of a new collection provided it is within the ±60 day window of that visit and it includes the results listed in Section 7.1.1.

α Imaging at Baseline and Month 24, and the associated pregnancy testing for adult females, may be waived for participants enrolled from locations other than the primary Clinical Centers/sites, or who are enrolled from an existing CC and qualify but are declining participation in the study because of imaging. Adult female participants will be asked to verbally confirm that they are not pregnant or planning to become pregnant during their time in study.

§ Imaging = low dose CT (adults); renal u/s (adolescents); imaging at 12 months considered standard of care procedure and not required. SOC imaging done at any point during the participant's follow-up will be collected and entered in the EDC database.

~ For Month 24, imaging performed for clinical care can be used in place of new imaging provided it was completed within ± 60 days of the visit, and the criteria in Section 7.1.1 are met.

|| Assessment of Lower Urinary Tract Symptoms in study participants aged ≥18 years using Comprehensive Assessment of Self-Reported Urinary Symptoms (CASUS)

7.4 CONCOMITANT MEDICATIONS, TREATMENTS, AND PROCEDURES

Participants in both arms will continue to receive clinical care from their treating urologist and/or nephrologist. Study participants will not be permitted to enroll in other trials of novel therapeutics to prevent or treat urinary stone disease.

Medications that reduce kidney stone recurrence are permitted in both arms. These medications include:

- 1) sodium or potassium citrate
- 2) thiazide diuretic
- 3) allopurinol

Any surgical procedure for treatment of a kidney stone is permitted. These procedures include:

- 1) ureteroscopy
- 2) shock wave lithotripsy
- 3) percutaneous nephrolithotomy

An outcome adjudication committee will adjudicate all procedures performed to determine if they were performed for a symptomatic stone, which is the primary outcome measure.

7.4.1. CHANGES IN PARTICIPANT CLINICAL STATUS OR TREATMENT DURING THE TRIAL

Analyses will adhere to an intention to treat principle, such that every attempt will be made to collect outcome information on all participants (even if the participant is unwilling or unable to adhere to the assigned intervention). It is possible that some participants may start new clinical regimens or develop new clinical conditions during the trial that were contraindications to enrollment. The following characteristics or treatments would require cessation of the intervention:

Incarceration, hyponatremia requiring medical intervention, and/or any condition preventing high fluid intake such as advanced CHF or cirrhosis with ascites.

The following characteristics or treatments would not require cessation of the intervention, but should be recorded by the study staff:

Study participants who develop struvite stones, cystine stones, or who started lithium use, diuretic use, topiramate use, ketogenic diet, chronic corticosteroid use, supplemental vitamin C; or develop recurrent UTIs.

Study participants who become pregnant during the study will be removed from the study with their pregnancy followed until final outcome (as described in 8.4.5).

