5.4 PARTICIPANT WITHDRAWAL OR TERMINATION

5.4.1 REASONS FOR WITHDRAWAL OR TERMINATION

Study participants may withdraw from study intervention or the entire study at any time during the study without prejudice. If a participant withdraws from study intervention, other study assessments will continue through the end of the study. The participant may be discontinued from study intervention at the discretion of the investigator if medically necessary or if any untoward effects occur. In addition, a study participant may be withdrawn by the investigator or the sponsor if the study participant violates the study plan or for administrative and/or other safety reason. Study coordinators will report reasons for study withdrawal in the EDC database.

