10 STATISTICAL CONSIDERATIONS

10.1 STATISTICAL AND ANALYTICAL PLANS

The statistical team at SDRC will perform the statistical analyses described in this section. An Intention-to-treat analysis will be performed and will serve as the primary analysis for the primary objective in this study. The Intention-to-treat cohort will include all randomized study participants.

In a separate document, a statistical analysis plan (SAP) will be developed by the SDRC team to include a comprehensive description of the statistical methods and analyses for the primary manuscript as well as the final study report. Prior to analysis, study population details, including the number of sites, the number of study participants in each study arm, and the number of study participants lost to follow-up will be described. Data for all randomized study participants, whether or not they completed all protocol requirements, will be included for analysis.

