10.4 DESCRIPTION OF STATISTICAL METHODS

10.4.1 GENERAL APPROACH

The primary analysis will be conducted by intention-to-treat principles. The analysis cohort for this study consists of all randomized study participants regardless of whether the study participant received the randomly assigned intervention strategy. All study participants who provide informed consent and who are randomized will be included in the analyses. For those study participants who are lost to follow-up, or who drop out of the study, the analyses will include all data up to the point of their last data collection whenever applicable. Safety data will be collected on all randomized study participants. All statistical analysis will be tested at two-sided nominal significance level of 0.05. If missing data constitute <2% of observations, the analysis will utilize single imputation (mean for continuous variables, mode for categorical variables). If missing data are >2% of observations, then the approach to missing data will depend on checks of the missing-at-random assumption, and will be detailed in the Statistical Analysis Plan.

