13.3 INFORMED CONSENT PROCESS

13.3.1 CONSENT PROCEDURES AND DOCUMENTATION

The clinical center Investigator has both ethical and legal responsibility to ensure that each study participant being considered for inclusion in this study is given a full explanation of the study. Informed consent will be obtained from all study participants (or their guardian or legally authorized representative [LAR]) before any study-related procedures (including any pretreatment procedures, such as preprocedure sedation) are performed or given.

Informed consent will be documented on an informed consent form (ICF), or through a remote consent process, that has been approved by the same IRB/EC responsible for approval of this protocol. The ICF will conform to FDA regulations in 21 CFR Part 50 and to the institutional requirements for informed consent and applicable regulations. The Investigator agrees to obtain approval from SDRC of any ICF intended for use in the study, before submission for IRB approval.

Consent will be obtained from the participant if age ≥ 18 years or parent/guardian consent if age < 18 years with adolescent assent, after all questions about study procedures have been addressed.

In addition, age-appropriate assent will be obtained from the pediatric study participants themselves. Informed consent is an ongoing process that takes place between the Investigator/study staff and study participants. In most cases, this process is initiated with informed consent at the start of the study; however, it also takes place as an ongoing dialogue between the Investigator/study staff and study

participants during the entire duration of their participation. Should the study participants become intolerant of any aspect of the study, their participation will be discontinued.

The approved consent process will be completed with the prospective study study participant or his or her LAR, and the Investigator or qualified designee will be available to answer questions regarding procedures, risks, and alternatives.

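### Three rules end study participation with no outcome follow-up afterwards, which conflicts with the protocol's own promise to collect outcomes on all participants

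*Combined protocol and SAP*

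**What the plan says.** The commitment is in 7.4.1: under intention to treat, "every attempt will be made to collect outcome information on all participants", and the text extends this to people who do not follow their assigned programme. Section 10.1 fixes the analysis set: "The Intention-to-treat cohort will include all randomized study participants". Section 5.4.1 separates stopping the intervention from leaving the study: "If a participant withdraws from study intervention, other study assessments will continue through the end of the study".

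Three other statements end participation itself:

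- **Pregnancy (7.4.1):** "Study participants who become pregnant during the study will be removed from the study with their pregnancy followed until final outcome".
- **Plan violation (5.4.1):** "a study participant may be withdrawn by the investigator or the sponsor if the study participant violates the study plan". The ground is not defined further.
- **Intolerance (13.3.1):** "Should the study participants become intolerant of any aspect of the study, their participation will be discontinued".

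After any early exit, 5.4.2 requests the Month 24 activities at the time of leaving and plans nothing later. For dropouts, 10.4.1 says "the analyses will include all data up to the point of their last data collection whenever applicable".

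**The concern.** The primary endpoint is time to first symptomatic stone event over 24 months. It can be followed through the quarterly remote questionnaires of 7.1.1 and medical records, so it depends on neither adherence nor study imaging. Ending follow-up because of pregnancy, a plan violation or intolerance therefore loses primary outcome data that could still be obtained.

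A log-rank test or Cox model treats a person removed at month 6 as if that person's later risk matched that of people who stayed. If removals are more frequent in one arm and those removed differ in stone risk, the comparison is distorted. A separate SAP can choose how to handle missing outcomes, but it cannot recover events that were never collected.

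**Working it through.** **1. The rules side by side**

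| Ground | Section | Force | Outcome collection after exit | Link to arm in the documents |
|---|---|---|---|---|
| Pregnancy | 7.4.1 | mandatory | pregnancy only | none |
| Plan violation | 5.4.1 | discretionary | none stated | none stated; plausible |
| Intolerance | 13.3.1 | mandatory wording, general consent section | none stated | none stated; plausible |
| Stopping the intervention only | 5.4.1 | participant's choice | continues to study end | not relevant |

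Only the last row fits the commitment in 7.4.1.

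**2. Why an arm link is plausible for two of the three.** In 6.1.1 the intervention arm must sync the bottle every day, while bottle use is optional for controls. The intervention arm also has a prescribed volume (4.1) and may receive coaching (6.1.3). It therefore has more ways to breach the plan or find it burdensome. Urine collections, imaging and questionnaires are common to both arms.

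**3. When bias arises (illustration).** From the documents: 15% control event rate at 2 years (10.5), 24 months of follow-up, and hazard ratio 0.7 (10.5) or 1.0 (the null, 10.2). Assumed: a share q of the intervention arm only is removed at 0.5 years, and the corresponding people in both arms have k times the hazard of the rest.

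Let h be the yearly hazard of the rest in the control arm, E(a,t) = 1 − exp(−a·t) and P(a,t) = E(a,t)/a.

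- Choose h so that (1−q)·E(h,2) + q·E(kh,2) = 0.15.
- Control rate = 0.15 / [(1−q)·P(h,2) + q·P(kh,2)].
- With g = h × true HR, intervention rate = [(1−q)·E(g,2) + q·E(kg,0.5)] / [(1−q)·P(g,2) + q·P(kg,0.5)].

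Example: q = 10%, k = 2, true HR 1.0. Then h = 0.0743. Control rate = 0.15/1.8457 = 0.0813. Intervention rate = 0.1314/1.7208 = 0.0764. Observed ratio = 0.0764/0.0813 = 0.940.

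Observed ratio when the true HR is 1.0:

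| k | q = 2% | q = 5% | q = 10% |
|---|---|---|---|
| 0.5 | 1.008 | 1.020 | 1.039 |
| 1 | 1.000 | 1.000 | 1.000 |
| 2 | 0.987 | 0.968 | 0.940 |
| 3 | 0.977 | 0.944 | 0.896 |

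When the true HR is 0.7:

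| k | q = 5% | q = 10% |
|---|---|---|
| 0.5 | 0.714 | 0.728 |
| 1 | 0.700 | 0.700 |
| 2 | 0.678 | 0.658 |
| 3 | 0.661 | 0.627 |

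With 821 per arm, q = 5% is about 41 people. If outcome follow-up continued after removal, this source of bias would be zero.

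**4. Power.** Section 10.5 states 1,642 participants for 80% power. Required events are 4(1.960 + 0.842)²/(ln 0.7)² = 247. Assuming uniform 2-year accrual and 2 further years of follow-up, this needs 1,329 people, and 1,329/0.8 = 1,661, within 3% of the stated figure. With each person followed for exactly 24 months, the requirement is 2,135 to 2,457. That discrepancy is a separate matter, so both designs are shown below.

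Power = Φ(√(D/4)·|ln 0.7| − 1.960), where D is the expected events at N = 1,642 with 20% exponential loss per 2 years. Extra removals x in both arms raise the loss to 1 − 0.8(1 − x).

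| Extra removals | Accrual design: events, power | Fixed 24 months: events, power |
|---|---|---|
| 0 | 260.0, 82.0% | 190.0, 69.1% |
| 5% | 250.9, 80.6% | 185.5, 68.0% |
| 10% | 241.8, 79.2% | 180.9, 67.0% |

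A few per cent of removals costs roughly one power point.

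**The case against.** A reader might infer more: that the trial will drop intervention-arm non-adherers, that the primary hazard ratio is then no longer an intention-to-treat estimate, and that it is pulled in favour of the programme. The documents do not support that.

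- Everyone randomized stays in the analysis set (10.1, 10.3, 10.4.1). What is lost is follow-up after exit.
- Missing fluid goals is an expected state with a planned pathway. Section 6.1.3 moves from problem solving to boosters to low-touch options for the rest of the study, keeps incentive eligibility, and gives retention as a reason for not prolonging intensive sessions. This suggests that few non-adherers would be withdrawn.
- Withdrawal for plan violation is discretionary. Intolerance also covers procedures that both arms share. Pregnancy has no stated link to arm, and 5.2 excludes women who are pregnant or planning pregnancy.
- The exit assessment in 5.4.2 can capture events up to departure.
- Direction depends on k. Equal risk gives no bias, and lower risk among those removed biases against the programme.

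All of this stands. On the other side, 6.1.2 and secondary hypothesis #6 associate low intake or urine output with higher stone risk, so k above 1 is a reasonable worry, though not a finding. The exit assessment says nothing about later events. The pathway in 6.1.3 also suggests that plan violation is not needed as a ground for ending follow-up, and 10.3 already handles major deviations through a per-protocol set.

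**Conclusion.** The conflict in the text is real. Section 7.4.1 contradicts itself on pregnancy, and 5.4.1 and 13.3.1 permit or require exits for which no outcome follow-up is planned. Those removed are censored at exit, with an avoidable loss of primary outcome data.

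The effect on the hazard ratio cannot be sized, because the documents give no removal rates and no risk profile for those removed. In the null illustration, the shift runs from about 0.10 in favour of the programme (10% removed, triple risk) to about 0.04 against it (10% removed, half risk), and is at most about 0.02 in either direction when 2% are removed. All of these figures assume removal from the intervention arm only, at month 6. A claim that the result is biased towards the programme goes beyond the evidence. The defensible statement is that the plan allows potentially informative censoring that it could prevent cheaply.

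**What to change.** Reconcile 5.4.1, 5.4.2, 7.4.1 and 13.3.1 on one question: whether outcome collection continues after each kind of exit. Whatever is decided clinically about the intervention and imaging, state that the quarterly remote questionnaires and record-based collection of stone events continue to month 24 unless the participant withdraws consent. Remove plan violation as a ground for ending outcome follow-up. While amending 7.4.1, correct its cross-reference for pregnancy: it cites 8.4.5, which covers hyponatremia, whereas pregnancy reporting is in 8.4.6.

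Section 5.4.1 already has coordinators record reasons for withdrawal. Tabulating them by arm in the final report would show how much this mattered.

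Cost: a protocol amendment and possibly a consent revision, each needing IRB approval under 13.2, plus a few more remote questionnaires. A person removed just after the month 6 contact would have six left (months 9, 12, 15, 18, 21 and 24). Under 8.4.6 pregnancies are already followed to their outcome, so some contact with those participants continues anyway.
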